A.3. Stress reduction as a target intervention for cannabis using women. Among chronic users of cannabis, stress has been shown to be a significant factor in initiation and maintenance of use (see Hyman & Sinha 2009 for review). For example, in a treatment seeking sample, Copeland and colleagues (2001) found stress relief to be the most commonly reported benefit from, and reason for continuing, cannabis use. Our group demonstrated that completion of a social stress task increased craving in individuals with CUD ([name] et al., 2011). Studies have also shown that cannabis users expect tension reduction from use (Galen & Henderson, 1999) and that coping motives are associated with levels of cannabis use (Bonn-Miller et al., 2007) and cannabis-related problems (Simons et al., 2005; Lee et al., 2007). Further, stress-related factors such as negative life events (Wills et al., 2001; Windle & Wiesner, 2004) and traumatic stress (Lipschitz et al., 2003; Bremner et al., 1996; Vlahov et al., 2004; Schiff et al., 2007) have demonstrated associations with cannabis use. It has therefore been suggested that interventions specifically focused on reducing, tolerating, and coping appropriately with stressors could improve treatment outcomes in cannabis users (Hyman & Sinha, 2009), and such an approach may have particular relevance for women.

Women report more severe negative affect symptoms and greater related functional impairment during cannabis withdrawal than men (Copersino et al., 2010; Hermann et al., 2015, Sherman et al., 2017). Studies in adolescents and young adults have indicated that females are more likely to use cannabis as a coping strategy for tension and stress (Simons et al., 1998; Terry-McElrath et al., 2009; Cuttler et al., 2016), whereas males often identify enhancing positive affect as a motive for cannabis use (Chabrol et al., 2005; Newcomb et al., 1998). Congruent findings have been demonstrated in human laboratory paradigms, with cannabis-using women reporting increased craving following stress tasks as compared to men (Buckner et al., 2011). Of note, exposure to trauma has been shown to impact stress responding in cannabis using women, but not men, suggesting that consideration of past traumatic experiences may be important in sex-specific treatment development (Chao et al., 2018).

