c. Remote screening visit alternative. Patients may also complete the initial visit remotely if warranted. In this case, subjects will be electronically consented through a secure platform such as Doxy.me or Redcap. The informed consent will be emailed to the participant prior to the video call. The patient will have the opportunity to ask questions on the call and will electronically sign the document. A signed copy will be emailed to the participant. The M.I.N.I interview and medical history then be conducted, also via Doxy.me. If clinically indicated, patients may have a physical exam the UDS visit. To date, no patients have been excluded due to physical exam findings. Patients will be advised to find a private location during these procedures to protect privacy and confidentiality. Patients will be sent survey links to complete self-report questionnaires.

d. Blood draws: In order to investigate the impact of moderate to heavy cannabis use and menstrual cycle on the endocannabinoid system, blood will be taken at Days 1, 8 and 22.

C.2.c.3. Progesterone Administration Procedures (Study Days 1-7). Following completion of screening procedures, participants will be scheduled to come to the clinic for training on CREMA and saliva (progesterone) collection procedures. The TLFB calendar will be completed. For female participants, menstrual history data will be used to schedule this session in the early follicular phase to standardize progesterone (or placebo) administration. During the early follicular phase, defined as the first 7 days after the onset of menses, ovarian hormones are low and largely invariant (approximately <1.1 ng/ml for progesterone and <85 pg/ml for estradiol; Chabbert-Buffet et al., 1998). This is critical for two reasons; first, to minimize the interaction between endogenous and exogenous sex hormones, and second, to achieve consistency between males and females as progesterone levels in men are steady and similar to levels observed in women during most of the follicular phase (Zumoff et al., 1990). At this visit, a urine sample will be collected to assess baseline cannabinoid level for purposes of cannabis abstinence verification (described below). Participants will be instructed to refrain from cannabis use during this study period.

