Participants will be provided with a seven-day supply of progesterone or placebo. Randomization to treatment will be done by the MUSC Investigational Drug Service (IDS). Dosing will begin in the evening on study day 1. On study days 2-7 participants will take medication at home in the morning and evening, and on day 8 the final dose will be taken at in the morning prior to completion of the laboratory stress task (described below). Progesterone and matching placebo capsules will be prepared and dispensed by the MUSC IDS. Previous studies (Fox et al., 2013; Sofuoglu et al., 2001; 2011) have used twice daily administration of 200mg progesterone during the early follicular phase to achieve stable levels of progesterone comparable to normal luteal phase levels (2-20 ng/ml). Safety and tolerability of micronized progesterone have been established in numerous studies with nicotine (Sofuoglu et al., 2001; 2011) and cocaine (Evans & Foltin, 2006; Fox et al., 2013; Reed et al., 2011 Sofuoglu et al., 2002; 2004) dependent individuals.

c. Cannabis Abstinence Verification. Cannabis abstinence will be assessed using self-report, saliva drug testing, and cannabinoid levels. Self-report will be collected at study visits using the TLFB as well as collected daily through mobile surveys or “morning reports” completed via mobile electronic device. Participants will be trained to self-administer saliva drug screening (Oratect FDA approved saliva test.). This test is able to detect THC in saliva for up to 14 hours. Participants will be instructed to complete two saliva drug tests daily using the RedCap video upload procedure described below under *Medication Adherence/Drug Test Monitoring*. A test will be completed in the office on Day 1 so patients can practice the procedure. Cannabinoid levels will also be assessed using urine toxicology collected on Study Days 8 and 22. Creatinine-corrected cannabinoid levels will be compared from Day 1 to Day 8 to confirm abstinence during the study period. Our group has recently published on the need for utilization of multiple methods to determine cannabis abstinence (Baker et al., in press). Contingency management (monetary compensation) procedures will be incorporated to promote abstinence (described below).

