At the start of each CREMA session, participants will be asked to stop using cannabis (if they are at the time), and provide ratings on craving, mood, and stress using a modified version of the Within Session Rating Scale (Childress et al., 1986). This visual analog scale is anchored with adjectival modifiers ("not at all, mildly, moderately, and extremely"). The scale includes items assessing anxiety, stress, irritability, and craving, and we have utilized it successfully in numerous previous studies. If the session is one of the two daily picture assessments, next a photograph (either stress-related or neutral) will be presented and the participant will be instructed to look at it carefully for 10 seconds. Each picture cue will appear only once during the study. An alarm will sound at the end of each trial, after which participants will complete a post-cue Within Session Rating Scale assessment, ratings of how carefully they looked at the photographs and their distraction level during each trial, and data on their cannabis use since last assessment. If the session is only collecting ambient stress and craving, immediately after the Within Session Rating Scale the participants will be asked to record data on cannabis use since the last assessment session. To encourage CREMA session completion, participants will be compensated \$5.00 for each completed session. Previous studies employing lower incentive strategies have reported 80-90% CREMA completion rates (Gass et al., 2012; Warthen et al., 2009), including in our previous SCOR (Wray et al., 2015); we have slightly increased compensation to maximize potential data collection over the 3-week period. CREMA sessions will begin on Day 2.

f. Progesterone Salivary Sample Collection. Participants will be instructed to collect a saliva sample each morning (1/2 hour after awakening). Samples will be dispensed into containers supplied by study staff and stored in participants' home freezers until bringing the samples to a subsequent study visit for analysis of progesterone levels. These daily home collection and storage procedures have been used in numerous previous studies with excellent participant adherence and sample quality (Edler et al., 2007; Klump et al., 2008). As discussed above in Preliminary Data, we successfully utilized a similar procedure in our last SCOR project. Participants will receive \$10 daily for collection of ovarian hormone salivary samples.

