g. Cannabis Withdrawal Assessment. The Cannabis Withdrawal Scale (CWS; Allsop et al., 2011) will be used to assess cannabis withdrawal symptoms, including negative affect and craving. CWS is a 19-item self-report measure that assesses withdrawal symptoms in the past 24 hours. The CWS will be administered twice daily during the progesterone administration phase as part of the RedCap medication adherence survey that will be sent via text message. Participants will be asked to respond with reference to the past 12 hours.

In order to assist participants with completing instruments and assessments at home, we will provide them with a link to an instructional video on YouTube and an FAQ sheet. These items will be emailed to participants after their Day 1 visit.

h. Cognitive Testing. Cognitive functioning will be assessed at BL and Study Day 8 to examine whether cognitive functioning is improved following progesterone administration and cannabis abstinence or whether changes in cognitive functioning mediate stress reactivity. Implicit cognitive function will be assessed using the Cannabis Approach-Avoidance Task (Jacobus et al., 2018; Sherman et al., 2018) which assesses the automatic tendency to approach rather than avoid drug cues, a cannabis adaptation of the dot-probe task that has shown sensitivity across substances of abuse (Field et al., 2006; Garland et al., 2013) which assesses cannabis attentional bias, and a cannabis adaptation of the Implicit Association Task (Wiers et al., 2011) which assesses cannabis memory bias. Explicit cognitive function shown to be impacted by SUDs will be assessed, including working memory – verbal (WAIS-IV Digit Span Subscale) and nonverbal (N-Back) (McClernon et al., 2016) tasks, and the Symbol Digit Modalities Test (SDMT) (Smith, 1982) which measures sustained attention, response speed, and visuomotor coordination.

As cognitive testing is not a primary outcome, it will not be completed at visit 1 or 8 when exposure needs to be limited for health and safety.

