queried three times daily regarding stress and craving levels (as assessed by the Within Session Rating Scale), as well as cannabis use in order to determine precipitants of, and sex differences in, return to use. As detailed above, two of these sessions will also include picture presentations (one neutral picture session and one stress-related picture session) to continue to assess stress reactivity during this period. Daily saliva samples will also be collected by participants as above. This monitoring will continue for two weeks following the laboratory stress session. At the end of the two weeks, on Day 22, participants will return to the clinic. At this visit, participants will return collected salivary hormone samples, provide a urine drug screen to validate self-reports of drug use, turn in any clinic-provided phones, complete a questionnaire regarding their experience with the CREMA and REDCap surveys, and be provided referrals to treatment if interested.

Participant Compensation: Participants will be compensated \$40 for completing the screening visit (\$20 for physical, \$20 for interview) and \$20 for Day 1. Participants will receive \$5 for each completed CREMA session, for a total possible compensation of \$300. Participants will receive a \$5 bonus for each day they complete all 3 sessions for a possible total of \$100. During the cannabis abstinence and progesterone administration period, participants can earn a total of \$120 for completing saliva tests \$360 for negative salivary drug tests and \$140 for completing medication adherence video uploads. Participants will receive \$190 for daily collection of salivary samples for ovarian hormone measurements. Participants will also be compensated \$100 for Study Visit 8 (\$50 if they re-schedule for Day 9) and \$100 for Study Visit 22, for a total potential compensation of \$1470. If they borrowed an iPhone and do not return it they will be paid \$50 for Visit 22. ClinCards may be mailed to participants or obtained at their first clinic visit. Participants will complete a w-9 which may be done in person or via Doxy.me.

Confidentiality: Confidentiality of all research data will be maintained by keeping all data in a locked file, limiting access to the computer database to only study personnel, and by using patient code numbers as opposed to names on all paperwork.

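### No withdrawal or craving rating is scheduled before abstinence and the first capsule, so the CWS and ambient-craving analyses forgo baseline adjustment and the planned sex comparisons lack a pre-cessation reference

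*Combined protocol and SAP*

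**What the plan says.** All references are to the Combined protocol and SAP.

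- **Start of abstinence and dosing.** In C.2.c.3, at the first clinic visit, "Participants will be instructed to refrain from cannabis use during this study period". Item b adds: "Dosing will begin in the evening on study day 1".
- **Day 1 visit.** Here "participants will be scheduled to come to the clinic for training on CREMA and saliva (progesterone) collection procedures". The section also lists the TLFB calendar and a urine sample, and C.2.c.2.d adds a blood draw. No symptom or cue rating is listed.
- **CREMA (item e).** "CREMA sessions will begin on Day 2". Every session opens with the Within Session Rating Scale. Picture sessions repeat it after the cue. One session a day shows no picture and records ambient stress and craving.
- **CWS (item g).** "The CWS will be administered twice daily during the progesterone administration phase as part of the RedCap medication adherence survey". On recall: "Participants will be asked to respond with reference to the past 12 hours".
- **Screening (C.2.c.2, items a and b).** The itemised instruments are the Quick Screen, M.I.N.I., menstrual diary, PSS, ACE, Coronavirus Impact Scale, TLFB, urine screen, breathalyzer and IDTS. None rates withdrawal or momentary craving. The Marijuana Craving Questionnaire and STAI are described only for the Day 8 laboratory session.
- **Analysis (C.2.d.1, Aim 1).** The centred pre-cue stress and craving rating is a time-varying covariate. No pre-treatment covariate is named. Post-hoc least-squares-mean comparisons of craving and stress between women and men over time are planned.

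**The concern.** Anxiety, irritability and craving are features of cannabis withdrawal, but they also vary between people who are not withdrawing. A score taken only after cessation mixes the two. Two things are at stake.

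The first is precision. For an outcome with no pre-dose value in the model, stable differences between people remain in the error term of the treatment and treatment x sex tests.

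The second is the reading of the sex comparisons. Sex is not randomised. Section A.3 motivates the trial partly on the ground that "Women report more severe negative affect symptoms and greater related functional impairment during cannabis withdrawal than men", and C.2.e justifies the dosing window by a peak of symptoms in the first 2-3 days. If women score higher during the abstinence week, the planned comparison cannot say whether that reflects a larger rise on stopping or a higher usual level.

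Other measures do get a starting value: urine cannabinoids and blood on Day 1, cognition at baseline, and two pre-stressor assessments on Day 8.

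**Working it through.** **1. Is there any rating before dosing?** The payment figures allow a check.
- CREMA: 300 / 5 = 60 sessions; 60 / 3 = 20 days, which matches Days 2-21. No paid session falls on Day 1.
- Adherence videos: the payment "for completing medication adherence video uploads" totals 140 at 10 each, so 14 videos = 1 (Day 1 evening) + 12 (Days 2-7) + 1 (Day 8 morning).

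A Day 1 evening survey is therefore implied, and it may carry a CWS whose 12-hour recall reaches back before the capsule. It still follows the abstinence instruction, is not required to precede the capsule, and is not named as a baseline. At best it is a near-baseline for the CWS. It gives none for the Within Session Rating Scale.

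**2. The plan's own sample size (C.2.d.3).** Inputs: d = 0.67 for treatment x sex (3.1 / 4.7), 80% power, 5% type 1 error (two-sided assumed), 32 per sex-by-arm cell, total 128.
- Simple comparison: n = 2 x ((1.960 + 0.842) / 0.67)^2 = 34.97, so 35 per cell. At 32 per cell, 0.67 x sqrt(32/2) = 2.68, and power = Phi(2.68 - 1.96) = 76.4%.
- With 7 daily ratings at autocorrelation 0.9: 34.97 x (1 + 6 x 0.9) / 7 = 34.97 x 0.914 = 31.97, so 32 per cell. This reproduces the figure, but the 0.9 is stated only for the Aim 3 calculation, so using it here is an assumption.

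**3. Standard error of the interaction.** For a difference of differences with 32 per cell, SE = SD x sqrt(4/32) = 0.354 SD, where SD is the within-cell value. This fits the plan's scale: sqrt(3.4^2 + 3.3^2) = 4.74, close to its 4.7.

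**4. Effect of one pre-dose covariate.** The documents give no correlation r, so a range is assumed. It applies to outcomes with no within-session covariate (CWS, ambient craving) and to full baseline coverage. Residual variance is multiplied by 1 - r^2 and the SE by sqrt(1 - r^2). The last column takes the plan's 80% as its start and assumes the same standardised effect for these outcomes; the plan sizes only the stress-cue outcome.

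| r | variance factor | SE (SD) | equivalent sample size, 1/(1 - r^2) | power at N = 128 |
|---|---|---|---|---|
| 0 | 1.00 | 0.354 | 1.00 | 80% |
| 0.3 | 0.91 | 0.337 | 1.10 | 83.6% |
| 0.6 | 0.64 | 0.283 | 1.56 | 93.8% |

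**5. Partial coverage.** If a share p of participants has a baseline and the rest enter through a missing-indicator, average residual variance is about 1 - p x r^2. Half coverage would halve the reduction, from 9-36% to 4.5-18%.

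**6. Cue reactivity.** Here r must be the correlation beyond the pre-cue rating already in the model. With assumed correlations of pre-cue with post-cue 0.7, baseline with pre-cue 0.5 and baseline with post-cue 0.45:

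partial r = (0.45 - 0.7 x 0.5) / sqrt((1 - 0.49)(1 - 0.25)) = 0.10 / 0.618 = 0.16; squared, about 0.03.

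On those values the extra reduction is about 3%.

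**The case against.** A reader might infer that Aim 1 as a whole fails because it cannot separate withdrawal from standing symptoms. The documents do not support that. Both Aim 1 hypotheses compare progesterone with placebo, by sex. Randomisation protects that comparison, and a sex difference present in both arms cancels from the interaction. No test of a withdrawal peak is planned; the 2-3 day statement explains when treatment is given.

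A reader might also infer that all standing stress and craving stays in the error of the primary cue-reactivity test. It does not. The pre-cue rating is a covariate and there is a daily neutral-picture session, so much of that variance is already removed. This stands, and it limits the precision argument to the CWS and ambient craving. The pre-cue rating is still no substitute for a baseline: it is recorded after dosing begins, so treatment may already have changed it.

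Other points on that side:
- The PSS is a pre-dose stress measure, but it measures a different construct and no model names it.
- Days 8-21 give ratings on the same scale after treatment. They are a partial reference for stress and craving, not for the CWS.
- Stratifying on anxiety disorder does not show that it is common. The stated reason is its influence on stress reactivity.
- The full analytic plan is in a Biostatistics Resource Core that was not supplied, and the study schematic mentions unspecified baseline measures. The Core could add a model term, but not a rating the protocol never schedules.
- Enrolment is under way (Version 16; C.2.d.3 refers to unusable early app data), so the full gain is no longer available.

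**Conclusion.** The point holds in a limited form. As scheduled, no CWS or Within Session Rating Scale rating precedes both abstinence and the first capsule, and no pre-treatment covariate is named for Aim 1. There is no bias in the randomised comparison. The cost is forgone precision for the CWS and ambient craving, plus a post-hoc comparison of women and men that cannot be read as a difference in withdrawal.

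The 9-36% variance reduction rests on an assumed r of 0.3-0.6 and complete baselines. It should not be read as the equivalent of 10-56% more participants for Aim 1 as a whole: coverage will be incomplete, and the gain for cue reactivity is probably much smaller. At r of 0.3 or below the gain is small even with full coverage. This is an optional improvement.

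**What to change.** At the Day 1 visit, before the first capsule:
1. Give the CWS and one Within Session Rating Scale. Optionally, score the CREMA training as one neutral and one stress session.
2. Record time since last cannabis use, because nothing in the schedule controls it and a rating soon after use may not reflect the usual level.

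In the analysis:
3. Enter the matching Day 1 value as a baseline covariate in the Aim 1 models, and read the comparisons of women and men relative to it.
4. For participants already enrolled, check whether the Day 1 evening survey included a CWS. Where it was completed before the capsule, use it as a near-baseline rather than an outcome, and identify it as such, since it was taken at home after the abstinence instruction.
5. Handle missing baselines with a missing-indicator or a constrained longitudinal model, so that nobody is dropped from the randomised comparison. State how many women and men have a baseline when reporting the sex comparisons.

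Cost: about 5-10 minutes at an existing visit and one model term. If the training is scored, each person sees one extra stress and one extra neutral picture. Baselines will remain incomplete for those already enrolled, and no cue baseline can be recovered for them.

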d. Medication Adherence/Drug Test Monitoring. Participants will record themselves taking their morning and evening medication doses as well as completing the twice daily saliva drug test swab procedure. Photos of the completed saliva test will be uploaded. A survey link will be sent to the participant’s (or study provided) cell phone via CREMA app alert twice daily. Video capture will occur as part of a RedCap survey. As discussed in the Preliminary Data section, we have previously utilized this technology successfully for both medication adherence monitoring and to remotely assess substance use. To encourage compliance with study procedures, participants will receive \$10 for completion of each medication adherence video. Participants will receive an additional \$30 for each saliva drug screen that is negative for all drugs of abuse. A similar compensation schedule was effective in our pilot progesterone study. Study staff will call participants twice during this week to see if they are having any difficulties with the procedures or side effects from the medication. Study staff will also text abstinence reminders to patients whose saliva tests positive for drugs of abuse.

e. CREMA Assessment. Cue Reactivity Ecological Momentary Assessment (CREMA; Warthen & Tiffany, 2009; Wray, Godleski, & Tiffany, 2011; Wray et al., 2015) is a cue reactivity assessment in which photographic stimuli are presented multiple times per day on a mobile electronic device (i.e iPhone). In cases where participants do not have a smart phone or do not wish to use their own device for the purposes of the study, a phone will be provided. Participants will be instructed to keep their phone with them at all times. Phones will be password protected to prevent access to the study assessments and surveys by anyone other than the participant. Auditory alarms will alert participants to complete three, randomly scheduled CREMA sessions per day (session duration = 3-4 minutes). Alarms will be distributed over a 12-hour period, divided into three, 4-hour blocks with a minimum time of 30 minutes between alarms/CREMA sessions. In order to accommodate varying participant wake-sleep schedules, participants will be able to choose the 12-hour period during which they will be prompted and this may vary from weekdays to weekends. There will be two types of picture cues that differ based on content:

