Data Management and Reduction: All paper-based assessments (other than laboratory reports) will be entered into REDCap, a secure, web-based application designed exclusively to support data capture for research studies. REDCap provides an intuitive interface for data entry (with data validation), audit trails for tracking data manipulation, and automated export procedures for data downloading to statistical packages such as SPSS and SAS. Quarterly database management and data integrity audits will be conducted.

C.2.d. Statistical Considerations

C.2.d.1. **Statistics and Data Analysis** (complete data analytic plan is provided in Biostatistics Resource Core)

Aim 1: Examine the impact of exogenous progesterone on stress cue reactivity and cannabis craving and withdrawal symptoms during a period of cannabis abstinence in the natural environment.

The primary measures of interest are stress and craving ratings in response to stress-related cues using Cue Reactivity Ecological Momentary Assessment (CREMA) in heavy cannabis using women and men. Hypothesis 1: Compared to placebo, progesterone will attenuate reactivity to stress cues presented in the natural environment among women vs. men with CUD. Hypothesis 2: Compared to placebo, progesterone will attenuate cannabis craving and withdrawal symptoms among women vs. men with CUD. To assess these hypotheses multilevel generalized linear mixed effects models with repeated measures (GLMMs) will be developed using CREMA session response data from the 1-week period during active medication administration. Pre-cue stress and craving rating will be centered and used as a time varying covariate in all analysis. Least squares means and associated standard errors will be used for post-hoc comparisons of cue response and CWS scores between treatment group assignments globally as well as time-specific (AM, PM) treatment group differences. Least squares means and associated standard errors will also be used for post-hoc comparisons of craving and stress response between women and men over time. Relevant interactions will be assessed in the models.

Aim 2: Examine the impact of exogenous progesterone on stress cue reactivity during a laboratory stressor task.

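### The first CWS score looks back over essentially pre-drug hours, but the Aim 1 text neither excludes it from the treatment comparison nor gives it a baseline role

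*Combined protocol and SAP*

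**What the plan says.** **Dosing** (C.2.c.3 b). The first dose is on Day 1: "Dosing will begin in the evening on study day 1". Two doses a day follow, through Day 7. The schedule then closes with a single dose: "on day 8 the final dose will be taken at in the morning prior to completion of the laboratory stress task".

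**CWS** (C.2.c.3 g). "The CWS will be administered twice daily during the progesterone administration phase as part of the RedCap medication adherence survey". The scale normally covers 24 hours; here the window is halved: "Participants will be asked to respond with reference to the past 12 hours".

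**Payment for adherence videos.** The rate in dollars is "10 for completion of each medication adherence video" (C.2.c.3 d). The maximum, also in dollars, is "140 for completing medication adherence video uploads" (Participant Compensation, after C.2.c.5).

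**Analysis** (C.2.d.1, Aim 1). Hypothesis 2 concerns craving and withdrawal in women versus men. Least squares means are to be used for "post-hoc comparisons of cue response and CWS scores between treatment group assignments globally as well as time-specific (AM, PM) treatment group differences". The models are tied to the week of active medication, but that wording refers to CREMA data. Pre-cue stress and craving ratings serve as covariates; no CWS value does. The section refers the reader to the Biostatistics Resource Core for the complete plan.

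The protocol text names no other baseline CWS and does not mention the Day 1 evening score separately.

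**The concern.** The survey that goes with the first capsule asks about the 12 hours leading up to that capsule. Whether the form is filled in just before or just after swallowing, almost all of that window is pre-drug. Participants are told to stop cannabis at the Day 1 visit (C.2.c.3, opening paragraph). The visit time is not given, so part of the window may also come before abstinence. C.2.e (ii) places peak withdrawal in the first two to three days of abstinence, so this score does not measure what Hypothesis 2 is about.

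If the score is averaged with the others, the estimated effect on withdrawal shrinks toward zero. The two time-of-day contrasts also stop being comparable, because the pre-drug score falls entirely in the PM set. Equal true AM and PM effects would then look unequal. And if the score's status stays unstated, it can be included, dropped or used as a baseline after the data are seen.

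**Working it through.** **1. Number of surveys.**
- From the dosing schedule: 1 (Day 1 evening) + 6 × 2 (Days 2-7) + 1 (Day 8 morning) = 14.
- From the payments: $140 / $10 = 14 videos. The two counts agree, so a dosing survey goes with the Day 1 evening dose, and the CWS is part of that survey.
- Split: PM on Days 1-7 = 7 scores; AM on Days 2-8 = 7 scores.

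**2. Pre-drug share.** One score in 14 overall (7.1%), one in 7 for PM (14.3%), none in 7 for AM.

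**3. Effect on the estimate.** Let m be the number of scores averaged with equal weight, one of them pre-drug. Randomisation makes the expected arm difference on that score zero. Let D be the average arm difference over the other m − 1 scores. The expected estimate is

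[(m − 1) × D + 0] / m = D × (m − 1)/m.

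| Contrast | Scores | Share of D estimated | Loss |
|---|---|---|---|
| Global | 14 | 13/14 = 92.9% | 7.1% |
| PM | 7 | 6/7 = 85.7% | 14.3% |
| AM | 7 | 7/7 = 100% | none |

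D is an average over time, so the ratio does not need a constant effect. The same ratios apply to the treatment-by-sex contrast. If the Day 8 morning score is treated as outside the one-week window, the global figure is 12/13 = 92.3%.

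**4. Power, as illustration only.** The protocol states no power for the CWS. Suppose a two-sided 5% test would have 80% power without the pre-drug score, which is a noncentrality of 2.80.
- Global: 2.80 × 13/14 = 2.60; power = Φ(2.60 − 1.96), about 74%.
- PM: 2.80 × 6/7 = 2.40; power = Φ(2.40 − 1.96), about 67%.

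Allowing for the slightly different variance of the mean (compound symmetry, assumed within-person correlation 0.5 to 0.9) gives 74.0-74.2% and 67.2-68.0%. Starting instead from the d = 0.67 and 32 per sex and arm in C.2.d.3, power is 76.4% without the score, 70-71% with it globally and 63-65% for PM (assumed correlation 0.3 to 0.9). That d comes from negative-emotion responses to stress cues in another population, not from the CWS.

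**The case against.** **Pooling is inferred.** A reader might conclude that the plan expressly averages the Day 1 evening score with the rest. It does not say so. It compares CWS scores globally and by AM/PM with no exclusion, and pooling is the plain reading of that. The unseen complete plan may define the set differently. This stands and limits the claim.

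**A Day 1 evening CWS might not exist.** The maximum of $360 at $30 per negative saliva test gives 12 tests, which fits Days 2-7 only, and CREMA sessions also begin on Day 2. But saliva tests are a separate count. The CWS is attached to the medication survey, and the dosing schedule and the video payments both give 14. The 12 does not displace that.

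**The model may not average.** With a treatment-by-time term, the Day 1 difference would appear as its own near-zero point, and the AM/PM differences could be read as contrasts at each occasion. Neither reading would dilute occasion-specific estimates. A global or PM average taken from such a model would still include the score. A covariance structure that weights occasions unequally would change the ratios.

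**The stakes are limited.** The named primary measures for Aim 1 are CREMA stress and craving ratings, which are unaffected. The AM/PM contrasts are post hoc, and no AM-versus-PM test is planned. All of this stands. A reader might also quote a drop in power from 80% to 74% or 67% as a property of this trial; the documents do not support that, since the starting value is assumed.

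**Conclusion.** The point holds as a modest gap in the definition of the CWS outcome. As written, the plan leaves an essentially pre-drug score among the on-treatment scores. An equally weighted average would then estimate 93% of the average on-drug effect globally and 86% for PM, with AM unchanged.

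This rests on three assumptions: that the Day 1 evening survey carries a CWS, which the dose and payment counts support; that the score is pooled, which is the plain reading but not an express statement; and that scores are equally weighted.

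The bias is toward no effect. It would be wrong to infer that it favours progesterone or placebo, because the pre-drug score should be balanced by randomisation, or that it reaches the CREMA outcomes. That part of the window precedes abstinence is possible but not shown. The change is worth making because it alters the estimate for a named hypothesis at almost no cost.

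**What to change.** In C.2.d.1, Aim 1, and in the Biostatistics Resource Core plan if it is silent, state that:

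- the on-treatment CWS outcome set runs from the Day 2 morning survey to the Day 8 morning survey, 13 scores (7 AM, 6 PM), which also settles that Day 8 morning is included;
- the Day 1 evening score is not an outcome;
- the Day 1 evening score enters the CWS models as the baseline covariate.

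In C.2.c.3 g, state that the Day 1 evening CWS is answered before the first capsule. The value is then collected after randomisation but before any drug, so treatment cannot have affected it.

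No new data are needed. The outcome set loses one score per person, with almost no loss of precision because the remaining 13 are correlated. Participants who skip the Day 1 evening survey will have no baseline, so the plan should say in advance how they are kept in the model, for example by filling in the covariate from the mean over both arms. The covariate may also gain precision. How much is unknown, because the documents give no correlation between this score and later ones.
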